#### 4.5.2. Immunogenicity Variables

Secondary and exploratory immunogenicity variables will be measured by the following assays:

- dmLT-specific serum IgG and IgA results as measured using ELISA will be reported by icddr,b lab for samples collected Days 1, 8, 15, 22, 29, 36, 57, and 114 for Oral and Sublingual Cohorts and at Days 1, 8, 22, 29, 43, 50, 71, and 128 for Intradermal Cohorts.
- IgG and IgA anti-dmLT Antibody Secreting Cell (ASC) results as measured using ELISpot will be reported by icddr,b lab for samples collected Days 1, 8, 15, 22, 29, and 36 for Oral and Sublingual Cohorts and at Days 1, 8, 22, 29, 43, and 50 for Intradermal Cohorts.
- IgG and IgA anti-dmLT Antibodies in Lymphocyte Supernatant (ALS) results as measured using ELISA will be reported by icddr,b lab for samples collected Days 1, 8, 15, 22, 29, and 36 for Oral and Sublingual Cohorts and at Days 1, 8, 22, 29, 43, and 50 for Intradermal Cohorts.
- Total fecal IgA and fecal anti-dmLT IgA results as measured using ELISA will be reported by icddr,b lab for samples collected Days 1, 8, 15, 22, 29, 36, and 57 for Oral and Sublingual Cohorts and at Days 1, 8, 22, 29, 43, 50, and 71 for Intradermal Cohorts.
- Total salivary IgA and the saliva-derived anti-dmLT IgA results as measured using ELISA will be reported by icddr,b lab for samples collected Days 1, 8, 15, 22, 29, 36, and 57 for Oral and Sublingual Cohorts and at Days 1, 8, 22, 29, 43, 50, and 71 for Intradermal Cohorts.
- Mucosal homing of IgG and IgA anti-dmLT ASC results as measured using ELISpot will be reported by icddr,b lab for samples collected Days 8, 22, and 36 for Oral and Sublingual Cohorts and at Days 8, 29, and 50 for Intradermal Cohorts.
- Serum toxin neutralizing antibody results as measured using Y-1 cell assay will be reported by the Center for Vaccine Development-Global Health (CVD) lab at the University of Maryland, Baltimore for samples collected Days 1, 8, 15, 22, 29, 36, 57, and 114 for Oral and Sublingual Cohorts and at Days 1, 8, 22, 29, 43, 50, 71, and 128 for Intradermal Cohorts.
- dmLT-specific IgG and IgA memory B cell results as measured using ELISpot will be reported by icddr,b lab for samples collected Days 1, 22, 36, 57, 114, and 209 for Oral and Sublingual Cohorts and at Days 1, 29, 50, 71, 128, and 223 for Intradermal Cohorts.
- dmLT-specific effector and memory T cell results as measured using CyTOF will be reported by the Cellular Immunology Group of the CVD for samples collected at screening and on Days 22, 36, 57, 114, and 209 for Oral and Sublingual Cohorts and at screening and on Days 29, 50, 71, 128, and 223 for Intradermal Cohorts.

## 5. SAMPLE SIZE CONSIDERATIONS

The sample size for each cohort was chosen based on the number of participants deemed appropriate for a Phase 1 study in which the vaccine has had limited experience by the different routes of administration in humans. Sample size was limited to at least 11 evaluable participants and up to 15 participants for each cohort (each of the nine planned cohorts A through I).

The DMID Data and Safety Monitoring Board (DSMB) was scheduled to review cumulative data after Cohorts A through F had completed safety data through 7 days post-third dose of vaccine. At which time each cohort had been expected to have at least 10 evaluable vaccinees (10 per cohort). Among the 10 vaccinees per dose, the absence of a dose-limiting AE provides for an upper 95% exact (Clopper-Pearson) confidence bound of 30.8%. The absence of a dose-limiting AE among 20 vaccinees per route (e.g., combining safety data from Cohort A and B) provides for an upper 95% confidence bound of 16.8%. If at the time of data review, there had been no dose-limiting AEs among 60 vaccinees (e.g., combining safety data from Cohorts A through F), this would have provided an upper 95% confidence bound of 6.0% (Table 4). There were no dose-limiting AEs among the 40 vaccinees (Cohort A through D) who received all three planned doses which provides an upper 95% confidence bound of 8.8%.

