5.3.3 Reasons for Withdrawal and Discontinuation of Dosing

A participant may voluntarily withdraw their consent for study participation at any time and for any reason, without penalty.

A participant may be withdrawn from study participation for any of the following reasons:

- Medical disease or condition, or any new clinical findings for which continued participation, in the opinion of the investigator, would compromise the safety or welfare of the volunteer, or would interfere with the volunteer's successful completion of the study, or would interfere with the evaluation of responses.
- Participant no longer meets eligibility criteria.
- As deemed necessary by the investigator for noncompliance or other reasons.
- Participant withdrawal of consent.
- Participant lost to follow-up.
- Participant dies.
- Termination of this study.
- New information becomes available that makes further participation unsafe.

The second or third dose of study product will not be administered for any of the following reasons:

- Medical condition for which continued participation, in the opinion of the investigator, would pose a risk to the participant or would likely confound interpretation of the results.
- Presence of signs or symptoms that could confound or confuse the assessment of reactogenicity. Study vaccination should be postponed/deferred until signs, symptoms, or acute illness have resolved and if within acceptable protocol-specified window for that visit. If outside this window, the DMID Medical Officer must first approve the vaccination and the documentation of approval should be filed in the research record.
- Any unresolved or continuing solicited or unsolicited Grade 3 AE deemed to be vaccine related until the time of next dose. An unresolved or continuing Grade 1 or 2 AE is

permissible unless, in the opinion of the investigator, it would render study vaccination unsafe or interfere with the evaluation of responses.

- Solicited or unsolicited Grade 3 AE that occurs without alternative etiology through 7 days following the previous vaccinations.
- Solicited AEs, the reactogenicity events occurring through 7 days of each vaccine:
 - Systemic reactions to include: feverishness (chills/shivering/sweating), fatigue (tiredness, malaise, general unwell feeling), myalgia (body ache, muscular pain) headache, diarrhea*, nausea*, vomiting* or abdominal discomfort*. Systemic reactions will also include the measurement of a daily oral temperature.

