#### **4.4.3. Method of Assigning Subjects to Treatment Groups (Randomization)**

The randomization code was prepared by the Statistical and Data Coordinating Center (SDCC), Emmes. Enrollment/randomization were performed through the enrollment module in the electronic data capture system, maintained by the SDCC.

For each cohort, eligible participants were randomized and assigned in a 4:1 ratio to dmLT (n = 12) or placebo (n = 3) groups. The randomization was based on a variable blocked scheme to provide an approximately balanced allocation to the treatment groups during the study.

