### 9.7.1 Sample Size

**Table 4: Sample Size/Probability Estimates**

	Evaluable Vaccinees (N)	Upper 95% Confidence Bound in the Absence of Observed Dose-Limiting AE
Per Cohort	10	30.8%
Per Route a	20	16.8%
Cohorts A-D b	40	8.8%
Cohorts A-F c	60	6.0%

aOral, sublingual or intradermalbReceived all three dosescPlanned prior to safety data review

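### The SAP's one observed safety bound (0 of 40, upper limit 8.8%) uses a completer-only denominator, and 40 does not reconcile with the 48 randomised to dmLT in Cohorts A-D

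*SAP*

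**What the plan says.** SAP Section 5 first gives planning bounds for zero events in 10, 20 and 60 vaccinees. It then turns to what happened: "There were no dose-limiting AEs among the 40 vaccinees (Cohort A through D) who received all three planned doses", with an upper 95% bound of 8.8%. Table 4 carries a Cohorts A-D row with N = 40 under a column for evaluable vaccinees, footnoted "Received all three doses".

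Other parts of the documents bear on that number:

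- **Randomised.** SAP 4.4.3 states that in each cohort "eligible participants were randomized and assigned in a 4:1 ratio to dmLT (n = 12) or placebo (n = 3) groups".
- **Planning minimum.** SAP Section 5 and Table 1 set it at 10 evaluable vaccinees per cohort. Protocol Section 4 defines evaluable as having had all three doses, with safety data and samples to at least 7 days after the third.
- **Stopping of dosing.** Protocol 5.3.3 lists, among the reasons for withholding dose 2 or 3, "Solicited or unsolicited Grade 3 AE that occurs without alternative etiology through 7 days following the previous vaccinations". It also lists a vaccine-related Grade 3 event that has not resolved by the next dose.
- **Safety population.** SAP 6.3.1 takes all eligible participants with at least one dose.
- **Doses given.** SAP 4.2 and 4.4.5 say Cohorts A-D had three doses. SAP Section 15 records missed third doses only for Cohort E, because of the lockdown.

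**The concern.** A bound on the rate of dose-limiting events should apply to people who start dosing. Here the denominator is people who finished. Under protocol 5.3.3, a vaccinee with a qualifying Grade 3 event after dose 1 or 2 gets no further dose, so cannot be among three-dose recipients. The denominator therefore depends partly on the outcome being counted, and it departs from the SAP's own Safety population.

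The count raises a second question. Forty is exactly 4 x 10, the planning minimum, yet it is worded as an observation, while 12 per cohort were randomised to dmLT. Neither document gives the numbers dosed or completing; the disposition shells read N=X. Neither defines a dose-limiting AE, so a reader cannot check the zero. At stake is a single sentence and a table row, but it is the only numerical safety result from trial data in the SAP, and it could be carried into the study report as it stands.

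**Working it through.** **Inputs.** Zero events in 40 vaccinees, bound 8.8% (SAP Section 5, Table 4). Planning minimum 10 per cohort, so 4 x 10 = 40. Randomised to dmLT 12 per cohort (SAP 4.4.3), so 4 x 12 = 48. The method is named at the n = 10 figure: "upper 95% exact (Clopper-Pearson) confidence bound of 30.8" (per cent).

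**Step 1: reproduce the SAP's figures.** With zero events in n, the two-sided 95% Clopper-Pearson upper limit is 1 - 0.025^(1/n).

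| n | Upper limit | SAP states |
|---|---|---|
| 10 | 30.85% | 30.8% |
| 20 | 16.84% | 16.8% |
| 40 | 8.81% | 8.8% |
| 60 | 5.96% | 6.0% |

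All four agree. A one-sided 95% limit (0.05 in the tail) would give 25.9%, 13.9%, 7.2% and 4.9%, so the SAP's bounds are the upper ends of two-sided intervals, though it does not say so.

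**Step 2: reading one, 40 is the planning minimum and all 48 completed.** The restriction then removed nobody. With zero events, 1 - 0.025^(1/48) = 7.40%. The stated 8.8% is too high by 8.8 - 7.4 = 1.4 percentage points, on the cautious side.

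**Step 3: reading two, 40 is a true completer count.** Then 48 - 40 = 8 vaccinees are outside the denominator, if all 48 were dosed. Their events are not reported, so a range is needed. For x events in 48, the upper limit is the p that solves P(X <= x | n = 48, p) = 0.025.

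| Events among 48 | Upper limit |
|---|---|
| 0 | 7.4% |
| 1 | 11.1% |
| 2 | 14.3% |
| 4 | 20.0% |

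If none of the 8 had an event, the result is again 7.4%. One event is enough to pass 8.8%. If some but not all of the 8 were dosed, zero events in 41 to 47 give 8.6% down to 7.55%.

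**Step 4: do the halting rules exclude reading two?** Not fully. For Grade 3 events, protocol 9.5 requires two participants in a cohort, or three within a route, with the same type of event. One vaccinee per cohort could be stopped under 5.3.3 without meeting that count, so progression through Cohorts A-D does not by itself show that nobody was stopped.

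**The case against.** The strongest reply is that nothing planned depends on this sentence. It sits in the sample-size section, and no hypothesis is tested. Adverse-event incidence, solicited-event intervals, and the counts of withdrawal and vaccination discontinuation all use the Safety population (SAP Section 9, Table 91). Table 10 shows how many received each dose, and Listing 1 gives the reasons for stopping. Anyone stopped by an adverse event will appear there. The completer condition is disclosed in both places and follows the protocol's definition of evaluable, which also explains why Cohort E is absent. All of this stands, and it limits the severity.

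It is also fair that the two complaints are alternatives. If all 48 completed, the restriction did no harm. The restriction can hide risk only if someone did not complete, and SAP 4.2, 4.4.5 and Section 15 give no sign of that in Cohorts A-D.

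Three stronger inferences are tempting and are not supported:

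- **That zero events was guaranteed.** Events after dose 3 would still count, and so would any event that did not stop dosing. With the term undefined, equating it with the 5.3.3 criteria is an assumption.
- **That 40 is certainly the planning figure.** The exact match with 4 x 10 and the statements in 4.2 and 4.4.5 make this plausible, but the SAP presents 40 as observed and gives no disposition counts to test it.
- **That 8 vaccinees were stopped by adverse events.** This would give 8/48 = 16.7% (95% CI 7.5 to 30.2%). No document reports such stops. Eight across two routes would put at least four in one route, and without meeting a halting rule the events would have to be of differing types. SAP 6.6.3 describes halting only as something that would have happened.

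The reply does not explain why 40 appears where 48 would be expected, or why a safety result is given on a denominator other than the SAP's own.

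**Conclusion.** The concern holds as a defect of denominator and labelling. The 8.8% is correct for 0/40. It bounds the rate among vaccinees who completed three doses, not among those who started, and the 40 is unreconciled with the 48 randomised to dmLT. The correction could move the number either way: to 7.4% if all 48 were dosed with no events, or to 11.1% with one event among those left out. The documents do not decide between these.

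The figures for 48 assume that every vaccinee randomised in Cohorts A-D had at least one dose. Protocol 5.3.4 allows replacements and additional participants, so the true count may differ. The 0/48 result further assumes no dose-limiting event outside the stated 40. Severity is minor to moderate: a stated number changes, but no planned safety analysis does.

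**What to change.** In SAP Section 5 and Table 4:

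1. Replace 40 with the observed number of dmLT recipients in Cohorts A-D with at least one dose, matching the Safety population in SAP 6.3.1.
2. Define a dose-limiting AE by reference to the dosing-stop criteria in protocol 5.3.3 and the halting criteria in protocol 9.5, as they already stand, and count such events after any dose.
3. Recompute the Clopper-Pearson limit and state that it is two-sided (7.4% if the result is 0/48).
4. Give the number completing three doses separately. If a completer-only bound is kept, label it as such.
5. Label the 10, 20 and 60 rows as planning values; at present only the 60 row's footnote says so.
6. Report Cohort E, which had two doses, on its own. A pooled A-E bound is not needed.

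The cost is a few sentences and one table, using disposition counts already planned for Tables 10 and 11. No new data or analyses are required.

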## 6. GENERAL STATISTICAL CONSIDERATIONS

### 6.1. General Principles

All continuous variables will be summarized using the following descriptive statistics: n (non-missing sample size), mean, standard deviation, median, maximum and minimum. The frequency and percentages (based on the non-missing sample size) of observed levels will be reported for all categorical measures. In general, all data will be listed, sorted by site, treatment and participant, and when appropriate by visit number within participant. Summary tables will be structured with a column (or row) for each treatment in the order from left to right (or top to bottom): Cohort A: Oral 5 µg dmLT, Cohort B: Oral 25 µg dmLT, All Oral Cohorts: Placebo, Cohort C: Sublingual 5 µg dmLT, Cohort D: Sublingual 25 µg dmLT, All Sublingual Cohorts: Placebo, Cohort E: Intradermal 0.3 µg dmLT, Cohort E: Intradermal Placebo. Where necessary, summary tables will be stratified with oral and sublingual cohort columns presented in one table and intradermal cohort columns presented in the table immediately following. Tables will be annotated with the total population size relevant to that table/treatment, including any missing observations.

### 6.2. Timing of Analyses be stratified by route of administration with a column for each

The final analysis will be performed after database lock. No interim analysis was planned or performed.

### 6.3. Analysis Populations

Summaries and analysis of safety data will be presented for the Safety Population. Summaries and analysis of immunogenicity data will be presented for the mITT and Per Protocol Immunogenicity Population. A tabular listing of all participants, visits, and observations excluded from the analysis populations will be provided in the CSR (Listing 4).

#### 6.3.1. Safety Population

The Safety Analysis population will include all eligible participants who received at least one dose of study product.

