ISM, MM, and the protocol PI will review Cohort A safety data collected through 7-days post vaccination of third dose of last participant for recommendation to proceed to the cohort B.						
B	B1 B2	Oral	25 placebo	12 3	10 1	1, 15, 29
C	C1 C2	Sublingual	5 placebo	12 3	10 1	1, 15, 29
ISM, MM, and the protocol PI will review Cohort C safety data collected 7-days post vaccination of third dose of last participant for recommendation to proceed to the cohort D.						
D	D1 D2	Sublingual	25 placebo	12 3	10 1	1, 15, 29
E	E1 E2	Intradermal	0.3 placebo	12 3	10 1	1, 22, 43
ISM, MM, and the protocol PI will review Cohort E safety data collected through 7-days post vaccination of third dose of last participant for recommendation to proceed to the cohort F.						
F	F1 F2	Intradermal	1.0 placebo	12 3	10 1	1, 22, 43
Scheduled DMID DSMB meeting will be held to review cumulative safety data through 7 days after the third dose of vaccine and determine if study should proceed to Cohorts G, H and I.						
G	G1 G2	Oral	50 placebo	12 3	10 1	1, 15, 29
H	H1 H2	Sublingual	50 placebo	12 3	10 1	1, 15, 29
I	I1 I2	Intradermal	2.0 placebo	12 3	10 1	1, 22, 43
Scheduled DMID DSMB meeting will be held to review the aggregate safety data through 28 days after the third dose of vaccine for all nine cohorts (A-I)						
A Final DMID DSMB meeting will be held to review the safety data following the completion of the study						

Note: the local DSMB will conduct a review of each cohort (A-I) by review of safety data through 7 days after the third dose of vaccine for each cohort. (see [Section 9.6.3](#)) The local DSMB will also be provided the final safety report, the same report that will be generated for the final DMID DSMB meeting.

* Evaluable participants are defined as completing all 3 doses of vaccine and providing both safety information and protocol-required specimens through at least 7 days after the third dose of

vaccine. Participants receiving at least one dose of the investigational product must be followed for safety until the end of the study. If additional participants are required, to maintain blinding, additional participants are to be determined by Emmes; to keep the blind, at least one placebo will be included.

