#### 6.3.2. Modified-Intention-To-Treat (mITT) Immunogenicity Population

The modified-intention-to-treat (mITT) immunogenicity population includes all eligible participants who received at least one dose of study product and contributed both pre- and at least one post-vaccination samples for immunogenicity testing for which valid results were reported.

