#### 6.3.3. Per Protocol (PP) Immunogenicity Population

The per protocol (PP) immunogenicity population includes all participants in the mITT subset with the following exclusions:

- Data from all available visits for participants found to be ineligible at baseline
- Data from all visits subsequent to major protocol deviations, such as:
  - Second or third vaccination not received
  - Second or third vaccination received out of window
  - Receipt of non-study vaccines during the timeframe prohibited by the protocol
- Data from any visit that occurs substantially out of window

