## 9. SAFETY EVALUATION

Safety listings will be sorted by treatment group, participant, and timepoint. N, Mean, Standard Deviation, Minimum and Maximum will summarize continuous safety variables, whereas number and percent will summarize categorical safety variables. Safety data will be summarized for the Safety Analysis Population.

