## 9.3. Adverse Events

When calculating the incidence of adverse events (i.e., on a per participant basis), each participant will only be counted once and any repetitions of adverse events within a participant will be ignored; the denominator will be the total population size. All adverse events reported will be included in the summaries and analyses.

An overall summary of adverse events by treatment group is presented in [Table 91](#) and [Table 92](#). Unsolicited adverse events occurring in more than 5% of participants in any treatment group are presented in [Table 93](#) and [Table 94](#).

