## 10.2 Protocol Deviations

**Table 5: Distribution of Protocol Deviations by Category, Type, and Treatment Group – Oral & Sublingual Cohorts**

Category	Deviation Type	Cohort A: Oral 5 µg dmLT (N=X)		Cohort B: Oral 25 µg dmLT (N=X)		All Oral Cohorts: Placebo (N=X)		All Oral Route Subjects (N=X)		Cohort C: Sublingual 5 µg dmLT (N=X)		Cohort D: Sublingual 25 µg dmLT (N=X)		All Sublingual Cohorts: Placebo (N=X)		All Sublingual Route Subjects (N=X)	
		No. of Subj.	No. of Dev.	No. of Subj.	No. of Dev.	No. of Subj.	No. of Subj.	No. of Dev.	No. of Subj.	No. of Dev.	No. of Subj.	No. of Dev.	No. of Subj.	No. of Dev.	No. of Subj.	No. of Dev.	
Eligibility/ enrollment	Any type																
	Did not meet inclusion criterion	x	x	x	x	x	x	x	x	x	x	x	x	x	x	x	x
	Met exclusion criterion																
	ICF not signed prior to study procedures																
	Other																
Treatment administration schedule	Any type																
	Out of window visit																
	Missed visit/visit not conducted																
	Missed treatment administration																
	Delayed treatment administration																
	Other																
Follow-up visit schedule	Any type																
	Out of window visit																
	Missed visit/visit not conducted																
	Other																

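### The Safety and mITT populations are limited to 'eligible' dosed participants; the word is undefined, conflicts with other parts of the plan, and read literally takes a dosed but ineligible participant out of the safety summaries

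*SAP*

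**What the plan says.** SAP 6.3.1 defines the Safety population: "The Safety Analysis population will include all eligible participants who received at least one dose of study product". Protocol 11.4.1 has the same definition, so the SAP did not introduce it. SAP 6.3.2 puts the same condition on mITT, which "includes all eligible participants who received at least one dose of study product and contributed both pre- and at least one post-vaccination samples" with valid results. SAP 6.3.3 builds the per protocol (PP) population from mITT and removes, among other things, "Data from all available visits for participants found to be ineligible at baseline". None of these sections defines 'eligible'.

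Four other places bear on the point:

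- SAP 9: "Safety data will be summarized for the Safety Analysis Population".
- SAP 9.3: "All adverse events reported will be included in the summaries and analyses".
- SAP Table 5 has an eligibility block with rows such as "Did not meet inclusion criterion". Its footnote sets N to the Safety Population.
- Protocol Table 1, footnote: "Participants receiving at least one dose of the investigational product must be followed for safety until the end of the study".

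Protocol 11.4.1 also says that mis-randomized participants are analysed, in every population, by the product they actually received. SAP 6.3 does not repeat that rule.

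**The concern.** A safety analysis should count everyone exposed. Here, membership of the Safety population depends on a condition that can be judged after exposure. Protocol 5.3.1 has eligibility confirmed before enrolment, but protocol 7.3 repeats an eligibility review after dosing (Visits 2, 4, 6, 7 and 8), and protocol 5.3.3 makes loss of eligibility a ground for withdrawal. With no definition of 'eligible', two programmers could build different Safety populations from the same sentence.

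The endpoints exposed are the solicited and unsolicited adverse events, whose tables take their N from the Safety population. Withdrawals and discontinued dosing also appear in the disposition tables (SAP Tables 10 and 11), where N is the number enrolled. With 12 vaccinees per cohort, one person can decide whether an event type appears in a table at all.

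**Working it through.** **Step 1. Two readings of 'eligible', set against the rest of the plan.** Reading A: a participant found ineligible after dosing is not eligible. Reading B: 'eligible' means cleared at enrolment.

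| Place | Under reading A | Under reading B |
|---|---|---|
| SAP 6.3.3, PP exclusion for ineligibility | Removes nobody, because mITT already lacks these people | Removes those cleared at enrolment and later found ineligible |
| SAP Table 5, eligibility rows with N = Safety Population | Counts deviations of people who are not in its N | Counts and N agree |
| SAP 9.3, which adverse events are summarised | Fails for any event in such a person | Holds |
| Protocol Table 1 footnote, follow-up of everyone dosed | Data are collected but not summarised | Data are collected and summarised |

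Reading A contradicts the first three rows. Reading B agrees with all four, but under it the word selects every dosed participant and so adds nothing. The table shells do not settle the matter. SAP Table 12 gives ineligibility as an example reason under PP, which favours B. It also has a block of exclusion reasons for the Safety population, and Listing 4 names Safety as an analysis from which a participant may be excluded, which leaves A open.

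**Step 2. The plan's own precision figures.** SAP 5 gives upper 95% exact bounds when no dose-limiting event is seen. For 0 of n, the two-sided Clopper-Pearson upper bound is 1 − 0.025^(1/n).

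| n | Computed | SAP 5 |
|---|---|---|
| 10 | 30.85% | 30.8% |
| 20 | 16.84% | 16.8% |
| 40 | 8.81% | 8.8% |
| 60 | 5.96% | 6.0% |

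All four reproduce to rounding. They rest on assumed numbers of vaccinees and do not depend on the population definition, so they are not in dispute.

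**Step 3. What one exclusion could do.** Input: 12 vaccinees per cohort (SAP 4.4.3). Assumption, not in the documents: one or two of them are dosed and later found ineligible.

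*No events in the group.* The upper bound is
- all 12 kept: 1 − 0.025^(1/12) = 26.5%;
- one dropped: 1 − 0.025^(1/11) = 28.5%;
- two dropped: 1 − 0.025^(1/10) = 30.8%.

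*One event in the group, and the dropped participant had it.*
- Everyone dosed: 1/12 = 8.3%. The exact lower limit is 1 − 0.975^(1/12) = 0.2%. The upper limit solves (1 − p)^12 + 12p(1 − p)^11 = 0.025, giving 38.5%.
- Literal definition: 0/11 = 0%, interval 0% to 28.5%.

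**The case against.** The strongest reply is that reading B was meant. The PP rule, Table 5 and SAP 9.3 all point that way, and enrolment requires confirmed eligibility. On that view this is loose wording and not a decision to discard exposed participants. As a statement of intent that is plausible. It does not repair the definition: no passage says that dosed participants later found ineligible stay in, and the safety summaries are tied to the population as defined. If reading B is intended, the word is redundant and removing it loses nothing.

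A reader might infer that the plan erases the events of such participants. The documents do not support that. SAP 6.1 says that data are in general all listed, SAP 6.3 and Listing 4 require exclusions to be shown, and Listing 22 gives unsolicited events by participant. What could be lost is a count in a summary table, not the record. Participant protection is also unaffected: the halting rules (protocol 9.5) carry no eligibility condition, and follow-up covers everyone dosed.

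A reader might also infer that exclusions would tend to fall on people with events, because the work-up of an event may uncover an exclusion condition. That is possible, but nothing in the documents bears on how often it happens, so no tendency can be claimed.

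Finally, the trial is descriptive, with no hypothesis test, and the intervals for 1/12 and 0/11 overlap widely. That limits the consequence. It does not make an eligibility condition suitable for a safety population.

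**Conclusion.** The point stands in limited form. The Safety and mITT definitions in both documents carry an undefined condition. Followed as written, it would take a dosed participant later found ineligible out of the adverse event summaries, and it contradicts SAP 6.3.3, SAP 9.3 and SAP Table 5. It should be corrected.

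The actual effect is unknown and may be zero, because the documents do not show that any dosed participant was ineligible. The change from 8.3% to 0% assumes one ineligible vaccinee in a group of 12 who also had the only event. Without an event, one exclusion moves the upper bound only from 26.5% to 28.5%. The stated sample size and precision figures are unaffected.

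**What to change.** - Delete 'eligible' from the Safety and mITT definitions in SAP 6.3.1, SAP 6.3.2 and protocol 11.4.1. Safety is then everyone who received at least one dose; mITT is everyone dosed who has valid pre-vaccination and post-vaccination results.
- Keep the exclusion for ineligibility in PP only. It then has an effect, and SAP 9.3 and Table 5 agree with the definitions.
- Carry the existing rule of protocol 11.4.1, analysis by product actually received, into SAP 6.3.
- Record the change in SAP 15, which at present lists only changes in conduct.

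The cost is one word in two definitions in each document, plus one sentence in the SAP. No table has to be redesigned. If no dosed participant was ineligible, the results do not change; if one was, that person stays in the primary safety summaries.
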